See Table A1 for the procedures and assessments to be performed for Month 12 visit. This visit will be conducted via a phone interview with the subject. A phone script will be provided to the study personnel to use when interviewing the subject. There will be a +/- window of 2 weeks for this visit.

A.16 Statistical Considerations

All subjects will be offered the re-infusion and formal statistical considerations regarding sample size and power are not provided. Based on prior studies, a second infusion of stem cells are safe but strict safety monitoring will be employed to continue the safety assessment of allogeneic infusion of MSCs. Detailed analyses will be described in the separate statistical analysis plan.

A.17 Safety Monitoring of 30-Day Rate of TE-SAEs

Monitoring of the rate of TE-SAEs by 30-days post-second infusion among subjects who received the infusion of allogeneic MSCs will be employed to assist the DSMB in prospective monitoring of this study. The guideline is to be used to indicate boundaries requiring discussion by the DSMB and is designed to assist the independent DSMB in overseeing the study. The DSMB may also request additional interim analyses and develop other criteria including provision for monitoring of potential late effects to determine when to intervene in the enrollment or treatment of subjects in the study. Monitoring of key safety endpoints will be conducted. If rates significantly exceed the pre-set threshold, then the DSMB will be notified.

A Bayesian motivated safety stopping guideline for monitoring the 30-day TE-SAE rate will be used for this trial. The expected underlying rate of TE-SAE at 30 days post-second infusion is assumed to be 13.3% based on the assumption that 2 out of 15 subjects experience a TE-SAE. It would then be assumed that a rate of greater than 40.0% is unacceptable.

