A Beta distribution can be used as the prior distribution of θ ; where θ is the proportion of subjects who experience an TE-SAE by 30-days post-second infusion. The stopping rule is based on the beta-binomial methodology and assumes a prior expected failure rate. This leads to prior Beta parameters where $a=0.8$ and $b=5.2$. The Beta distribution will have a prior mean of 0.13 and a prior probability of <0.05 of exceeding 0.40. The guideline is derived such that there is strong evidence (posterior probability >0.95) that the probability of the event is greater than 40%, the trial will be stopped. The resulting boundaries tabulated in Table A2 were rounded to be conservative with the stopping guideline and is considered after 5 subjects are enrolled on the study.

TABLE A2

Bayesian Stopping Guideline for Event Rate of 13% *

# Events	# Subjects in Study
3	5
4	6-9
5	10-14
6	15

* The stopping guidelines serve as a trigger for consultation with the DSMB for additional review, and are not formal “stopping rules” that would mandate automatic closure of study enrollment.

A simulation study was conducted to evaluate the operating characteristics of this stopping rule. Data were generated from the binomial distribution with varying probabilities of failure (θ) and assuming a sample size of 15 subjects. Table A3 shows the probability of stopping the trial early and the average sample size (N), conditional on stopping early, at which the boundary is crossed for each value of θ . The unconditional average sample size of the trials for each value of θ is displayed.

Table A3

Operating Characteristics for Bayesian Motivated Stopping Guideline

Mean of Prior Distribution	θ	Probability of stopping	Conditional Average Sample Size (N)	Unconditional Average Sample Size of Trials (N)
0.13	0.13	0.05	8.4	14.7
	0.18	0.12	8.8	14.2
	0.23	0.25	8.9	13.5
	0.28	0.40	8.8	12.5
	0.33	0.56	8.5	11.4
	0.40	0.75	8.0	9.8

Although the motivation for the boundary is Bayesian, the operating characteristics can be evaluated from a frequentist perspective of Type I error and power. The stopping rule for a 13% event rate has a 5% chance (“Type I error”) of suggesting early termination when the true rate is 0.13, and a 75% chance (“power”) when the true rate is 0.40.

Limitations

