A major limitation to the second infusion approach is the small sample size. While it is assumed that all 15 subjects will be eligible for a second infusion, there is a chance that subjects will not want to undergo a second infusion and thus would further limit the amount of information received. However, the second infusion strategy is being implemented to obtain information on the safety of a second infusion of allogeneic MSCs to help guide future studies.

Addendum B: Penicillin/streptomycin free cell safety study

B.1 Rationale and Description for penicillin/streptomycin free cell safety study

This addendum to the protocol is designed to gain additional safety of penicillin/streptomycin free intravenous infusion of allo-hMSCs in subjects with aging frailty. Up to twenty subjects will be recruited to participate in a single dose of allogeneic MSCs in this follow-on phase. All study specific processes and procedures included in the protocol apply in this addendum unless otherwise noted. This population will not be included in the main phase of the trial, which included 15 pilot and 30 randomized subjects. Additionally, subjects receiving a dose in the penicillin/streptomycin free study are eligible to receive up to three (3) additional infusions.

B.2 STUDY OBJECTIVES AND ENDPOINTS

B.2.1 Study Objectives

B.2.1.1 Primary Objective

1. Demonstrate the safety and tolerability of penicillin/streptomycin free intravenous infusion of allo-hMSCs in subjects with aging frailty.

B.2.1.2 Secondary Objectives

6. To explore treatment efficacy (decrease in frailty, frequency of acute exacerbations, change in symptom related quality of life, improved cardiovascular status, decrease in inflammatory biomarkers, endothelial function and 1 year survival).

B.2.2 Study Endpoints

B.2.2.1 Primary Endpoints (Safety)

1. Safety (Primary): Incidence (at one month post second infusion) of any treatment-emergent serious adverse events (TE-SAEs), defined as the composite of: death, non-fatal pulmonary embolism, stroke, hospitalization for worsening dyspnea and clinically significant laboratory test abnormalities, determined per the Investigator's judgment.

- Laboratory tests included in the primary endpoint include the following:

- Serum chemistry: chloride, sodium, Carbon Dioxide, BUN, creatinine, glucose, calcium, AST/SGOT, ALT/SGPT, total bilirubin (fractionate if total >1.5 times normal), alkaline phosphatase, albumin,

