The Month 12 visit will be waived if screening visits for subsequent infusions take place prior to this visit.

B.15 Statistical Considerations

All subjects will be offered the penicillin/streptomycin free hMSCs and formal statistical considerations regarding sample size and power are not provided. Based on prior studies, stem cells are safe but strict safety monitoring will be employed to continue the safety assessment of penicillin/streptomycin free allogeneic infusion of MSCs. No detailed analyses will be described in the statistical analysis plan.

B.16 Safety Monitoring of 30-Day Rate of TE-SAEs

Monitoring of the rate of TE-SAEs by 30-days post infusion among subjects who received the infusion of penicillin/streptomycin free allogeneic MSCs will be employed to assist the DSMB in prospective monitoring of this study. The guideline is to be used to indicate boundaries requiring discussion by the DSMB and is designed to assist the independent DSMB in overseeing the study. The DSMB may also request additional interim analyses and develop other criteria including provision for monitoring of potential late effects to determine when to intervene in the enrollment or treatment of subjects in the study. Monitoring of key safety endpoints will be conducted. If rates significantly exceed the pre-set threshold, then the DSMB will be notified.

A Bayesian motivated safety stopping guideline for monitoring the 30-day TE-SAE rate will be used for this trial. The expected underlying rate of TE-SAE at 30 days post-infusion is assumed to be 10% based on the assumption that 2 out of 20 subjects experience a TE-SAE. It would then be assumed that a rate of greater than 40.0% is unacceptable.

A Beta distribution can be used as the prior distribution of θ ; where θ is the proportion of subjects who experience an TE-SAE by 30-days post infusion. The stopping rule is based on the beta-binomial methodology and assumes a prior expected failure rate. This leads to prior Beta parameters where $a=0.8$ and $b=5.2$. The Beta distribution will have a prior mean of 0.13 and a prior probability of <0.05 of exceeding 0.40. The guideline is derived such that there is strong evidence (posterior probability >0.95) that the probability of the event is greater than 40%, the trial will be stopped. The resulting boundaries tabulated in table B2 were rounded to be conservative with the stopping guideline and is considered after 5 subjects are enrolled on the study.

TABLE B2

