Bayesian Stopping Guideline for Event Rate of 10% *

# Events	# Subjects in Study
3	5
4	6-9
5	10-14
6	15

* The stopping guidelines serve as a trigger for consultation with the DSMB for additional review, and are not formal “stopping rules” that would mandate automatic closure of study enrollment.

A simulation study was conducted to evaluate the operating characteristics of this stopping rule. Data were generated from the binomial distribution with varying probabilities of failure (θ) and assuming a sample size of 15 subjects. Table B3 shows the probability of stopping the trial early and the average sample size (N), conditional on stopping early, at which the boundary is crossed for each value of θ . The unconditional average sample size of the trials for each value of θ is displayed.

Table B3
Operating Characteristics for Bayesian Motivated Stopping Guideline

Mean of Prior Distribution	θ	Probability of stopping	Conditional Average Sample Size (N)	Unconditional Average Sample Size of Trials (N)
0.13	0.13	0.05	8.4	14.7
	0.18	0.12	8.8	14.2
	0.23	0.25	8.9	13.5
	0.28	0.40	8.8	12.5
	0.33	0.56	8.5	11.4
	0.40	0.75	8.0	9.8

Although the motivation for the boundary is Bayesian, the operating characteristics can be evaluated from a frequentist perspective of Type I error and power. The stopping rule for a 13% event rate has a 5% chance (“Type I error”) of suggesting early termination when the true rate is 0.13, and a 75% chance (“power”) when the true rate is 0.40.

Limitations

A major limitation to this approach is the small sample size. However, the penicillin-streptomycin free infusion strategy is being implemented to obtain information on the safety of a penicillin/streptomycin free allogeneic MSCs to help guide future studies.

Addendum C: Pilot and Penicillin/Streptomycin Free Subjects Optional Follow-on Phase

C.1 Rationale and Description of additional infusions for subjects who have received one or two infusions in the phase I open-label phases of this protocol.

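### B.16 sets out a 10%, 20-subject safety rule but carries Addendum A's 13.3%, 15-subject tables, and in A.17 and B.16 the written 40% criterion does not generate the printed boundary

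*Combined protocol and SAP*

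**What the plan says.** Addendum B (B.1) sets the cohort size: "Up to twenty subjects will be recruited to participate in a single dose of allogeneic MSCs in this follow-on phase". In B.16 the expected 30-day TE-SAE rate "is assumed to be 10% based on the assumption that 2 out of 20 subjects experience a TE-SAE", and Table B2 is captioned for a 10% rate.

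The rest of B.16 describes something else. The prior is Beta(0.8, 5.2): "The Beta distribution will have a prior mean of 0.13 and a prior probability of <0.05 of exceeding 0.40". The operating characteristics were simulated "assuming a sample size of 15 subjects. Table B3 shows the probability of stopping the trial early". Table B2 ends at subject 15, Table B3 starts at a true rate of 0.13, and the closing sentence gives 5% and 75% for a rule with a 13% event rate. The prior, the four boundary rows and every figure in Table B3 match A.17 (Tables A2 and A3), where the rate "is assumed to be 13.3% based on the assumption that 2 out of 15 subjects experience a TE-SAE".

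Both addenda state the same criterion. A.17 requires "strong evidence (posterior probability >0.95) that the probability of the event is greater than 40%, the trial will be stopped". B.16 says the guideline applies when "there is strong evidence (posterior probability >0.95) that the probability of the event is greater than 40" percent, and adds: "The resulting boundaries tabulated in table B2 were rounded to be conservative with the stopping guideline".

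**The concern.** There are two separate inconsistencies.

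The first is in B.16 only. The expected rate and the table caption were changed for the new cohort, but the calculation was not. A quarter of the planned subjects (16 to 20) have no boundary, and the false-flag rate at the stated 10% is not given.

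The second is in A.17 and B.16. The rule in words and the rule in the table are not the same. A DSMB member working from the text would apply a far less sensitive rule than one working from the table.

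Safety is the primary objective of the penicillin/streptomycin-free cohort, and Table B2 is its only tabulated trigger for the TE-SAE rate. B.15 says the SAP will hold no detailed analyses for this cohort, so the correction cannot be expected there.

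**Working it through.** **Inputs.** Prior Beta(0.8, 5.2) (A.17, B.16). Printed boundary: 3 events at 5 subjects, 4 at 6–9, 5 at 10–14, 6 at 15 (Tables A2, B2). N = 15 (A.17) and up to 20 (B.1). Rates 2/15, 2/20 and 40% (A.17, B.16). Looks are taken after every subject from the fifth unless stated. That schedule is an assumption; it reproduces Table B3.

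**Formulas.** After k events in n subjects the posterior is Beta(0.8 + k, 5.2 + n − k). For the operating characteristics, f_n(k) = (1 − θ) f_{n−1}(k) + θ f_{n−1}(k − 1). At each look the mass s_n at or above the boundary is removed. Flag probability P = Σ s_n; conditional average N = Σ n·s_n / P; unconditional average N = Σ n·s_n + N(1 − P).

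**1. Reproduce the plan.** Prior mean 0.8/6 = 0.133 and P(θ > 0.40) = 0.049, as stated. Printed boundary, N = 15:

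| θ | Flag, exact | Flag, Table B3 | Uncond. N, exact | Uncond. N, Table B3 |
|---|---|---|---|---|
| 0.13 | 0.044 (0.048 at 2/15) | 0.05 | 14.7 | 14.7 |
| 0.18 | 0.123 | 0.12 | 14.2 | 14.2 |
| 0.23 | 0.245 | 0.25 | 13.5 | 13.5 |
| 0.28 | 0.397 | 0.40 | 12.5 | 12.5 |
| 0.33 | 0.556 | 0.56 | 11.4 | 11.4 |
| 0.40 | 0.750 | 0.75 | 9.8 | 9.8 |

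Table B3 is therefore right for the printed rows and 15 subjects.

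**2. Printed boundary, 20 subjects.** Flag probabilities do not change, because no row exists beyond 15: 1.9% at 0.10, 4.4% at 0.13, 75.0% at 0.40. Unconditional average N does change. At 0.40 it is 0.7503 × 8.04 + 20 × 0.2497 = 11.0, not 9.8. At 0.13 it is 0.0441 × 8.46 + 20 × 0.9559 = 19.5, not 14.7. With a look after every subject the row at 15 never acts: 6 events at 15 require at least 5 at 14, which already crosses. All flagging ends by subject 14.

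**3. Test the written criterion.** P(θ > 0.40) at the printed boundary:

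| Events/subjects | 3/5 | 4/6 | 4/9 | 5/10 | 5/14 | 6/15 |
|---|---|---|---|---|---|---|
| Posterior | 0.33 | 0.48 | 0.24 | 0.36 | 0.14 | 0.22 |

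None is near 0.95. Applied literally, 5/5 gives 0.80 and 7/7 gives 0.93, so no flag is possible before subject 8 (8/8 gives 0.959). At 15 it needs 12 events (11 gives 0.933, 12 gives 0.974); at 20 it needs 14 (13 gives 0.910, 14 gives 0.959). At a true rate of 40% it flags with probability 0.0055 (N = 15) or 0.0114 (N = 20).

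**4. What does generate the rows.** P(θ > 2/15) > 0.95 returns every printed row. This rule is inferred from the table; neither addendum states it. Carried on, it gives 6 events at 16–20, although 6/20 passes only narrowly (0.9502).

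**5. Rows carried to 20 under that rule.** Flag probability is 2.4% at 0.10, 6.1% at 0.13 and 89.2% at 0.40. The gain at 0.40 (0.892 − 0.750, about 14 points) comes entirely from subjects 16–20. Average N at 0.40 moves only from 11.0 to 10.8.

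**6. Sparser looks.** With looks assumed at 5, 10, 15 and 20 only, the printed table flags 1.1% at 0.10 and 64.7% at 0.40 (19.6 points of this at subject 15, so that row can then act). Carried to 20 it flags 1.8% and 88.2%.

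**The case against.** The practical stakes are limited. The footnote to Table B2 makes it a trigger for DSMB consultation, with no automatic stop. Through B.11, section 8.2.4 also applies: one qualifying related, unexpected SAE within 30 days puts accrual and treatment on hold, TE-SAE monitoring does not end at subject 15, and the DSMB may add criteria. At a true rate of 10% the printed table flags less often than the quoted 5%, so no excess of false alarms is hidden. C.1 reports that all 20 subjects of this cohort, and 12 subjects given two doses, had already been treated. All of this stands, and it makes the point mainly one of correct documentation and reporting.

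The 89.2% is also one reading of an unstated rule. Thresholds from about 0.132 to 0.137 all return the printed rows. Above about 0.1335 the row at subject 20 becomes 7, and the flag probabilities become 2.2%, 5.5% and 86.4% at 0.10, 0.13 and 0.40. The value 2/15 is the natural choice because A.17 states it, but the figure is conditional on it. About 2.8 of the 14 points gained arise at subject 20, when everyone has been dosed, and the 30-day window delays other flags. The gain is therefore not all protection of later subjects.

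Neither argument removes the contradictions. The conservative rounding mentioned in the text cannot turn 12 of 15 into 6 of 15.

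**Conclusion.** Both inconsistencies are confirmed. The 5% and 75% quoted in B.16 are properties of the printed rows at true rates of 13% and 40%, with unconditional sample sizes that hold for 15 subjects only. They do not describe a plan stated as 10% and 20 subjects, for which the printed rows give 1.9% at 10% and average sizes near 20 when the rate is low. In A.17 and B.16 the written criterion and the table are different rules: 0.5% to 1.1% against 75% at a true rate of 40%.

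The figures for the printed rows and for the written criterion assume a look after every subject. The figures for rows carried to 20 also assume the inferred 2/15 threshold. The documents give no look schedule for this cohort, and DSMB review is roughly quarterly (section 9.3). The missing rows lower the flag probability at 40% under either schedule examined. This should be fixed; confidence is high.

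**What to change.** 1. Reconcile the expected rate (10% or 13.3%) across B.16's text, prior, Table B2 caption and closing sentence.
2. Reconcile the written 40% criterion with the rule behind the table, in both A.17 and B.16.
3. Carry Table B2 to 20 subjects under the reconciled rule, state the look schedule, and requote Table B3 for N = 20 with a 0.10 row.
4. As the subjects have been dosed, report the corrected figures with the results of each addendum, and do not quote 5% and 75% as properties of a 10%, 20-subject plan.

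The choice of threshold is for the sponsor and DSMB. The arithmetic consequences at N = 20, with a look after every subject, are:

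| Choice | Boundary | Flag at 0.10 | Flag at 0.40 |
|---|---|---|---|
| 13.3% and inferred rule | printed rows, then 6 at 15–20 | 2.4% | 89.2% |
| 10% reference, same prior | 3 at 5–8, 4 at 9–14, 5 at 15–20 | 7.7% | 95.9% |
| 10% reference, illustrative Beta(0.6, 5.4) | 3 at 5–7, 4 at 8–13, 5 at 14–19, 6 at 20 | 6.1% | 94.2% |
| 10% reference, illustrative Beta(0.8, 7.2) | 3 at 5–6, 4 at 7–12, 5 at 13–19, 6 at 20 | 5.2% | 93.8% |
| Written 40% criterion, same prior | none before 8, then 8/8, rising to 12/15 and 14/20 | about 0 | 1.1% |

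For the first choice, Table B3 would read (flag probability, conditional N, unconditional N): 0.10: 0.02, 10.5, 19.8; 0.13: 0.06, 11.3, 19.5; 0.18: 0.18, 11.9, 18.6; 0.23: 0.36, 11.9, 17.1; 0.28: 0.55, 11.5, 15.3; 0.33: 0.73, 10.8, 13.3; 0.40: 0.89, 9.6, 10.8.

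The cost is two small tables in B.16 and one reconciled sentence in each addendum. If the criterion is settled in favour of its wording, Tables A2 and A3 must be recomputed as well. No extra subjects or data are needed.
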